# Specific Aim III: To investigate the impact of preemptive Contact Precautions for residents of long-term care facilities admitted to acute care units, including the impact on the rate of hospital acquisition of MDRO and C. difficile and unintended consequences (e.g. frequency of HCP contacts, patient falls) due to this isolation strategy.

**SIGNIFICANCE:** One factor that may impact the effectiveness of the PPE used to prevent transmission of pathogens like MDROs and *C. difficile* centers upon the initial decision to implement these precautions. Specifically, patient selection for isolation precautions could lead to transmission if persons harboring these pathogens are not considered for placement into isolation. With the increasing prevalence of MDROs and *C. difficile*, specific patient populations at greater risk for infection and/or colonization with these organisms have been identified. One such patient population is residents of long term care facilities (LTCF). LTCFs are important reservoirs of MDROs, including MRSA, extended-spectrum beta lactamase (ESBL) producers, MDR *Acinetobacter*, and *C. difficile*. A prospective cohort study evaluating transmission dynamics of MDR gram-negative bacteria (MDRGNB) among LTCF residents during one year of follow up found that 39% of residents acquired at least 1 MDRGNB. A subsequent study evaluating 360 LTCF residents with advanced dementia demonstrated high rates of MDRO colonization at baseline (any MDRO = 45.6%, MDRGNB = 36.9%, MRSA = 12.8%). The proportion of all residents colonized at some point over a 12 month period was even higher: any MDRO, 66.9%; MDRGNB, 54.4%; and MRSA, 27.1%.

When they are admitted to acute care facilities, these patients become an important source of MDRO and C. difficile transmission. In a study evaluating the inter- and intradissemination of MDRGNB among LTCF residents with advanced dementia, genetically-related MDRGNB strains were detected in residents of 82% (18/22) of LTCFs indicating interdissemination between these facilities. The authors concluded that MDRGNB are spread both within and between LTCFs among residents with advanced dementia and that infection control measures should target this high-risk group of residents. A model of MRSA outbreaks in a LTCF demonstrated both direct and indirect effects of LTCF resident transfers on acute care facilities' MRSA prevalence indicating the role of transmission and need for hospitals to address LTCF in their infection control strategy. CRE can be spread extensively throughout a diverse healthcare facility network, highlighted nicely by the involvement of 14 acute care hospitals, 2 long-term acute care facilities, and 10 LTCFs during an outbreak in a single community. C. difficile shares similar risk factor and reservoir considerations as MDROs with the LTCF populations. Data suggest that C. difficile infection is endemic in LTCFs and remains largely uncontrolled despite numerous efforts to manage the issue. The incidence rate (2.3 cases/10 000 resident-days) and recurrence rate (1.0 case/10 000 resident-days) of C. difficile infection in LTCFs is comparable to that of acute-care hospitals.

At present, Contact Precautions are routinely employed in acute care facilities for patients colonized or infected with MDROs or *C. difficile*. The decision to place a patient into these precautions is often based on the results of clinical or surveillance cultures positive for these pathogens. Notably, this practice may only identify patients at a time point after they have potentially exposed HCP, staff, and other patients. In addition, surveillance cultures obtained on patient admission is a controversial infection prevention strategy and may not be performed in some hospitals. Even in those facilities that do perform such screening, testing for all important MDROs is rare and often not practical. Because of this, some have endorsed different

approaches to the identification of patients who may require Contact Precautions. As part of its Guidance for Control of CRE, the CDC noted that "extensive inter-facility sharing of patients across the continuum of care has the potential to facilitate widespread regional transmission of CRE." The guidelines then suggest as a supplementary practice to standard infection control practices the placement into preemptive Contact Precautions patients transferring from high-risk settings, which may include LTCFs. Data are lacking to evaluate if this is a reasonable strategy. A review in *Clinical Microbiologic Review* stated, "[u]pon admission of patients at increased risk of CRE carriage (such as residency in an LTCF . . . ), preemptive isolation while awaiting surveillance culture results can prevent early transmission events." Preemptive Contact Precautions have been suggested for certain high risk groups in extenuating circumstances for other pathogens such as MERS-CoV  with the understanding that targeting high risk populations could mitigate pathogen transmission.

Such an empiric isolation strategy, however, may have unintended consequences. Previous studies have demonstrated that patients placed into Contact Precautions may have more adverse events, depression and delirium, and potentially worse patient satisfaction and quality of care. A prospective cohort study in four acute care facilities performing active surveillance for MRSA demonstrated that Contact Precautions were associated with activities likely to reduce transmission of MDROs such as fewer visits and better hand hygiene at exit, while simultaneously exposing patients to less HCP contact, less visitor contact and other unintended outcomes. In contrast, a recent trial of universal gown and glove use in ICU settings assessed adverse event rates in these units and found patients were no more likely to experience adverse events than in control ICUs.

For study Aim III, we will investigate the impact of preemptive Contact Precautions for residents of LTCFs admitted to acute care units on the rate of hospital acquisition of MDROs and *C. difficile*. We will also examine the potential for unintended consequences (e.g. frequency of HCP contacts, patient falls) due to this isolation strategy.

**INNOVATION:** Most Contact Precautions used in non-epidemic settings target patients with demonstrated MDRO or C. difficile infection or colonization detected through surveillance and/or clinical cultures. Our proposed study will preemptively target a population with a high risk exposure (LTCF residence). This approach has been suggested by CDC as a possible measure to reduce transmission of MDROs, but little evidence exists to support its use. A preemptive isolation approach would be logistically easy to implement operationally as there would be minimal delay in identifying patients who require isolation compared with the historical approach of culture-based practices. A preemptive isolation approach for high risk patients would be a horizontal infection control program, which would be a paradigm shift in terms of identifying those at risk and implementing control programs to reduce transmission. From a populationbased perspective, horizontal infection control programs that substantially reduce all infections at a certain site is more impactful than a program than one that targets a single organism at that site. Unintended consequences of Contact Precautions have been evaluated in several populations, but never specifically for LTCF residents. Any impact seen through a preemptive isolation strategy must be balanced with any unintended consequences. If this study demonstrates a decrease in hospital-onset (HO) MDRO/C. difficile infections and does not show an increase in non-infectious complications (i.e. patient falls), then it has the potential to be a new strategy for reducing pathogen transmission in acute care settings.

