#### **RESEARCH DESIGN AND METHODS:**

**Study design:** Pre-post withdrawal quasi-experimental study using interrupted time series analysis.

**Study sites:** Six inpatient medical units within Vanderbilt University Hospital will serve as study units. These have been selected due to a higher rate of HO-MDRO/*C. difficile* incidence and/or a higher proportion of admissions comprising LCTF patients. The proposed acute care units have an average of 4,952 patient days per month with LTCF residents comprising 4.3-5.6% of unit admissions. This percentage is likely an underestimation because not all places of patient origin are documented and transfers between units within VUH are not included in this analysis. The HO-MDRO/*C. difficile* rate of these 6 units combined was 4.62 per 1,000 patient days for 2014.

**Study procedures:** After a 6 month baseline period, all units will be transitioned to a 6 month intervention period where all patients transferred onto the study units with LTCF origin prior to admission will be placed on preemptive Contact Precautions (Figure 5). Both patients admitted directly to a study unit as well as patients transferred from a non-study unit onto a study unit will be included under the policy. A washout period of 2 weeks will be introduced before a post-intervention withdrawal period of 6 months is implemented.

Inclusion/exclusion criteria: All patients admitted to the unit will be included in the study. There will be no exclusion criteria.

**Primary outcome - Rate of hospital-onset MDRO and** *C. difficile* **infections:** Aggregate rates of all hospital-onset (HO)-MDRO infections (Table 3), including MRSA, *C. difficile*, VRE, ESBL+ GNB, CRE, and MDR *Acinetobacter*, on participating units will be calculated. As active surveillance for these pathogens is not performed at VUH, only culture specimens obtained for clinical decision making will be included. Specimens from any site (e.g. blood, urine, wound) will be included. These events will be captured daily using the Vanderbilt Infection Prevention Electronic Resource (VIPER), an HAI surveillance platform that monitors laboratory results in real time. Events will be classified as HO if the specimen was collected >3 days after admission to VUH (i.e. on or after day 4).

Secondary outcomes:

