#### 1) Unintended consequences:

**a. Patient fall rates:** All patient falls are reported and recorded as a part of the VUH quality program using the National Database of Nursing Quality Indicators (NDNQI) definitions and process. As per NDNQI, a fall is defined as "an unplanned descent to the floor or other lower surface with or without injury to the patient that occurs in an eligible nursing unit." All events are reviewed and categorized based on the degree of patient injury/harm, if any occurred. The fall rate per 1,000 patient days for the aggregate study unit population will be measured. In addition the rate of falls with harm (as defined by NDNQI) will also be assessed.

**b.** Fall events in patients placed in the preemptive intervention: In addition to the aggregate fall rates for the study units, the frequency and number of falls (as defined by NDNQI) that occur in patients placed into preemptive isolation will be captured.

**c. HCP contact with patients placed in the preemptive intervention**: Trained study personnel will audit HCP contact (time spent, # of encounters) for all patients placed into preemptive isolation as previously described. As a proxy of HCP frequency of contact, the number of vital signs recorded per patient day will also be analyzed.

MDRO Type	Defined as
MRSA	Staphylococcus aureus resistant to oxacillin or methicillin by standard susceptibility testing methods
VRE (vancomycin- resistant enterococci)	Enterococcus faecalis, Enterococcus faecium, or other Enterococcus species that is resistant to vancomycin
CRE (carbapenem- resistant Enterobacteriaceae)	Any Escherichia coli, Klebsiella oxytoca, Klebsiella pneumoniae, or Enterobacter spp. testing resistant to imipenem, meropenem, doripenem, or ertapenem by standard susceptibility testing methods OR by production of a carbapenemase (i.e., KPC, NDM, VIM, IMP, OXA-48) demonstrated using a recognized test (e.g., polymerase chain reaction).
MDR (multidrug resistant)- Acinetobacter	Any Acinetobacter spp. testing non-susceptible (i.e., resistant or intermediate) to at least one agent in three or more classes of antibiotics (excluding nitrofurantoin, tetracyclines, 1st and 2nd generation cephalosporins, and non- extended-spectrum penicillins)

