ESBL + GNB (extended-spectrum beta-lactamase producing gram- negative bacillus)	Any E. coli , K. pneumoniae and K. oxytoca demonstrated to have ESBL activity based on results from BD Phoenix through microdilution methodology. The BD Phoenix performs ESBL testing using cephalosporins (ceftazidime/cefotaxime/ceftriaxone) + clavulanic acid.

Table 3:	Definitions	of MDROs	Included in	Primar	y Study	y Outcome
----------	-------------	----------	-------------	--------	---------	-----------

2) Subgroup examinations of individual pathogen HO-infection rates for the overall study population and the aggregate HO-MDRO/*C. difficile* infection rate for each individual study unit

**Covariates:** Several factors may affect the impact of the intervention on the primary outcome. These will be measured and included in the analysis.

**1) Hand hygiene compliance:** Study unit compliance with hand hygiene as monitored by the Vanderbilt Hand Hygiene Program^34 will be included for analysis.

2) PPE compliance: Trained study personnel will perform audits of PPE use by HCP caring for patients placed into the preemptive intervention.

**3) Antimicrobial utilization:** Use of broad-spectrum antibiotics is currently tracked as a part of the VUMC Antibiotic Stewardship Program (Co-directed by Epicenter investigator [name]). Because antibiotic use is a factor in the acquisition of MDROs and *C. difficile*, we will include a measure of broad-spectrum antimicrobial use in the analysis (measured as days of therapy [DOT]).

**Analysis:** The rates of the primary and secondary outcomes will be compared for the following phases, defined *a priori*: 6 month baseline period, 6 month intervention period, and 6 month withdrawal period. In addition, a more robust interrupted time-series regression analysis with Newey-West standard errors will be performed using bimonthly outcome rates (which will provide 12 separate time point measurements for each period).

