**Sample size considerations:** Existing data were used to assess sample size adequacy. Using patient-days, the mean patient days per period will be 4,952 patient days/month for a total of 29,710/period. The rate of HO-MDROs on the units of interest is 4.6/1000 patient days for an average of 137 evaluable events per period. This study will have 80% power to detect a true difference in infection rates of 1.4/1000 patient days. That means a reduction by approximately 42 events in the intervention period. Nursing home admissions (those that will receive the intervention) are at least 4.3-5.6% on target units which is likely an underestimate given the current reporting system.

**Safety:** A data safety monitoring board (DSMB) will be created to oversee any potential adverse events that would require further assessment and intervention. At present 100% of falls, including all falls with harm, have an event review as part of the VUH quality program. The current fall rate on the four proposed units is 2.6 falls/month. The DSMB will review the event analysis of all falls on the unit on a quarterly basis with more in depth interim analysis of all falls stratified by study intervention. Due to the low rates of baseline falls, there is the potential for low case counts to cause large percentage increases, making a pre-defined threshold difficult for stopping the trial. If a sustained, significant increase in falls is seen and thought to be due to the Contact Precautions intervention, then the study will be halted.

**Limitations and future directions:** The evaluation of preemptive Contact Precautions for patients with LTCF exposure will be conducted in an academic, tertiary referral hospital with high rates of hand hygiene compliance. Preemptive isolation is a supplementary strategy and may not be generalizable to acute care hospitals with suboptimal hand hygiene compliance. If an impact on HO infections is seen during the intervention without unintended consequences, then there may be other high risk epidemiologic groups that could benefit from preemptive isolation. If this trial shows a reduction in HO-MDRO rates, this strategy may benefit from a larger-multicenter trial with randomization. This study has the potential to transform how isolation policies are implemented in acute care hospitals and could reduce the risk of pathogen transmission to other HCP and their patients.

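### Aim III lets the mere absence of a shown rise in falls serve as the safety half of the case for preemptive isolation, with no margin or confidence bound

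*Protocol*

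**What the plan says.** The Innovation section of Specific Aim III sets a two-part condition for taking the policy forward. Hospital-onset infections must be shown to decrease, and the study must be one that "does not show an increase in non-infectious complications (i.e. patient falls), then it has the potential to be a new strategy". Limitations and future directions restates it: "If an impact on HO infections is seen during the intervention without unintended consequences, then there may be other high risk epidemiologic groups" that might gain from the same policy.

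Falls are a secondary outcome: "The fall rate per 1,000 patient days for the aggregate study unit population will be measured". Falls with harm and falls among isolated patients are also recorded, the latter without a named comparison group. Outcome rates are compared across a "6 month baseline period, 6 month intervention period, and 6 month withdrawal period".

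The only fall count is in the Safety paragraph: "The current fall rate on the four proposed units is 2.6 falls/month". The Study sites paragraph says "Six inpatient medical units within Vanderbilt University Hospital will serve as study units", with "LTCF residents comprising 4.3-5.6% of unit admissions". The sample size paragraph covers infections only. The Safety paragraph recognises that falls are few, but uses this only to explain why no stopping threshold is set in advance.

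**The concern.** The two halves of the condition carry different burdens of proof. The infection half needs a demonstrated effect. The falls half is met by non-detection, and non-detection is easy when events are few. The protocol states no margin, no interval and no precision for falls, so nothing separates a reassuring result from an uninformative one.

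The patients exposed to any harm from isolation are a small fraction of the population in which the fall rate is measured, so harm to them is heavily diluted. The protocol itself cites reports of more adverse events and less staff contact under Contact Precautions, and notes that such effects have not been studied specifically in long-term care residents. At stake is a statement that the policy works without unintended consequences, made when the data are compatible with a material rise in falls.

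**Working it through.** **Plan's own figure (infections).** Inputs from Sample size considerations: 29,710 patient-days per period and 4.6 events per 1,000. Events: 4.6 × 29.71 = 136.7, stated as 137. Difference: 1.4 × 29.71 = 41.6, stated as about 42. Power, taking two Poisson rates and an assumed two-sided 5% level: SE = √[(0.0046 + 0.0032)/29,710] = 0.000512; 0.0014/0.000512 = 2.73; Φ(2.73 − 1.96) = 78%. The difference detectable with 80% power is 1.43 per 1,000, which rounds to the stated 1.4. The figure reproduces. There is no counterpart for falls.

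**Expected falls per six-month phase.** The text does not settle whether 2.6/month is a total or per unit, or whether four or six units apply:
- total: 2.6 × 6 = 15.6
- total, scaled to six units: 15.6 × 6/4 = 23.4
- per unit, four units: 2.6 × 4 × 6 = 62.4
- per unit, six units: 2.6 × 6 × 6 = 93.6

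**Reading 1: an increase is shown only by a significant test.** Falls are treated as Poisson counts X₀ (baseline) and X₁ (intervention) over equal exposure. Given n = X₀ + X₁, X₁ is Binomial(n, r/(1 + r)) for a true ratio r. The condition is met unless the exact two-sided test of r = 1 gives p < 0.05 with X₁ > X₀. Probability that it is met:

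| Falls per phase | r = 1 | r = 1.05 | r = 1.5 | r = 2 |
|---|---|---|---|---|
| 15.6 | 98% | 98% | 81% | 42% |
| 23.4 | 98% | 97% | 71% | 23% |
| 62.4 | 98% | 96% | 32% | <1% |
| 93.6 | 98% | 95% | 15% | <1% |

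**Harm confined to isolated residents.** If a share s of falls occurs in them, the aggregate ratio is 1 + s × (their ratio − 1). Assume s equals their share of admissions, 0.043 to 0.056. A doubling then gives 1.043 to 1.056, and the condition is met 98% of the time at 15.6 falls and 95-96% at 93.6.

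Sensitivity: if residents fall k = 2 to 3 times as often as others, s becomes k·s/(k·s + 1 − s), about 0.08 to 0.15. A doubling then gives ratios of 1.08 to 1.15, and the condition is met 85-97% of the time.

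Comparing residents alone does not rescue it. Expected falls are 15.6 × 0.043 = 0.7 up to 23.4 × 0.056 = 1.3 per phase, and a doubling is missed more than 98% of the time. At 93.6 falls in all (4.0 to 5.2 in residents) it is missed 81-86% of the time.

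**Reading 2: an increase is shown by a higher observed count.** The condition is met when X₁ ≤ X₀. With no harm this has probability 51-54% over the four readings; with r = 1.05 it is 48% at 15.6 falls, falling to 38% at 93.6. For unit-wide harm at 15.6 falls it is 12% (r = 1.5) and 1% (r = 2).

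**What a bound would show.** With equal observed rates, the one-sided 95% upper limit is p/(1 − p) times the exposure ratio, where p is the Clopper-Pearson upper limit for X₁/n. This gives 1.91 for 16 v 16 falls, 1.70 for 23 v 23, and 1.52 for 23 v 47 with baseline and withdrawal pooled (2 × 23.4 = 46.8).

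**The case against.** A reader might infer that the study will declare preemptive isolation free of harm and that real harm would almost always slip through. The documents do not support that reading.

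- The language is conditional. The policy would only have potential, results are to be balanced against unintended consequences, and a larger randomised trial is the suggested next step.
- The protocol never says that showing an increase means reaching significance. If it means a higher observed count, unit-wide harm would seldom pass.
- Even under a significance test, a unit-wide doubling passes only 42% or 23% of the time at the lower counts, and on the largest reading a 1.5-fold rise passes only 15%. So the condition does discriminate for large unit-wide harm.
- There is no settled planned fall count on which to base a single miss rate.
- Harm assessment is wider than one comparison: falls with harm, audited staff contact, vital-sign frequency, quarterly event review by the DSMB and provision to halt.
- A margin or interval for a secondary outcome could sit in a statistical analysis plan, and a pass/fail margin here is debatable.

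These points limit the claim but do not remove it. None of the other measures supplies an upper bound on the fall rate ratio. The criterion at issue is stated in the protocol itself, in two places. Under neither reading does the aggregate comparison say much about harm confined to the isolated patients.

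**Conclusion.** The concern holds in a limited form. As written, failure to show a rise in falls is allowed to support the policy, and at these counts it cannot carry a no-harm statement.

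For unit-wide harm the weakness depends on how 2.6 falls/month is read: serious if it is a total, modest for a 1.5-fold rise if it is per unit on six units. For a doubling confined to isolated residents the weakness persists throughout. Under a significance test it passes about 95-98% of the time, against about 98% with no harm. On observed counts it passes about 38-48%, against 51-54%.

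This rests on independent Poisson falls, equal exposure in each phase, an assumed two-sided 5% level, and residents' share of falls equal to their share of admissions. The protocol thinks that admission share is probably understated. If residents also fall more often than others, detection improves, but only to a pass rate of 85-97% over the range examined.

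**What to change.** In Innovation and in Limitations and future directions, replace both conditions with a commitment to report the fall rate ratio, intervention against baseline and withdrawal pooled, with its upper confidence limit. State that increases up to that limit are not excluded. Make no no-harm statement unless the limit lies below a margin that the sponsor and DSMB fix before the intervention starts; otherwise describe falls as descriptive only. The second option meets the objection to a formal margin on a secondary outcome.

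Reconcile the four units in the Safety paragraph with the six in Study sites, and state whether 2.6 falls/month is a total or per unit.

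The cost is wording and one interval, with no new data. The downside is that the study will probably be unable to claim safety from falls and would have to say so.
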